#### 9.5.1.3 Pharmacokinetic Assessments

Not applicable.

#### 9.5.1.4 Pharmacodynamic Assessments

Not applicable.

#### 9.5.1.5 Pharmacogenomic Assessments

Whole blood samples for preparation of genomic DNA may be obtained at baseline from subjects for additional exploratory analyses.

#### 9.5.1.6 Safety Assessments

Safety assessments will consist of monitoring and recording all AEs and serious adverse events (SAEs); discontinuation from treatment, prior and concomitant medication usage, periodic measurement of weight, and assessments of cognitive functioning and monitoring of suicidal thoughts or depressive symptoms. The C-SSRS will be administered at specified intervals.

##### **9.5.1.6.1 ADVERSE EVENTS AND EVENTS ASSOCIATED WITH SPECIAL SITUATIONS**

An AE is any untoward medical occurrence in a subject or clinical investigation subject administered an investigational product. An AE does not necessarily have a causal relationship with the medicinal product. For this study, the study drug is perampanel.

The criteria for identifying AEs in this study are:

- Any unfavorable and unintended sign (including an abnormal laboratory finding), symptom, or disease temporally associated with the use of an investigational product, whether or not considered related to the investigational product (Note: A sign or symptom should not be listed as a separate AE if the applicable disease [diagnosis] is being reported as an AE)
- Any new disease or exacerbation of an existing disease
- Any deterioration in nonprotocol-required measurements of a laboratory value or other clinical test (eg, electrocardiography or x-ray) that results in symptoms, a change in treatment, or discontinuation of study drug
- Recurrence of an intermittent medical condition (eg, headache) not present at pretreatment (ie, at baseline)

An abnormal laboratory test result should be considered an AE if the identified laboratory abnormality leads to any type of intervention, withdrawal of study drug, or withholding of study drug, whether prescribed in the protocol or not.

All AEs observed during the study will be reported on the eCRF. All AEs, regardless of relationship to study drug or procedure, should be recorded beginning from the time the subject signs the study ICF through the last visit. Subjects who fail screening primarily due to AE(s) must have the AE(s) leading to screen failure reported on the Screening Disposition eCRF. SAEs will be collected for 28 days after the last dose.

Abnormal laboratory values should not be listed as separate AEs if they are considered to be part of the clinical syndrome that is being reported as an AE. It is the responsibility of the investigator to review all laboratory findings in all subjects and determine if they constitute an AE. Medical and scientific judgment should be exercised in deciding whether an isolated laboratory abnormality should be classified as an AE. Any laboratory abnormality considered to constitute an AE should be reported on the Adverse Event eCRF.

It is the responsibility of the investigator to review the results of the C-SSRS in all subjects and determine if any result constitutes an AE. Medical and scientific judgment should be exercised in deciding whether an isolated suicidality rating scale response should be classified as an AE.

All AEs must be followed for 28 days after the subject's last dose, or until resolution, whichever comes first.

Every effort must be made by the investigator to categorize each AE according to its severity and its relationship to the study treatment.

### **Assessing Severity of Adverse Events**

AEs will be graded on a 3-point scale (mild, moderate, severe) and reported in the detail indicated on the eCRF. The definitions are as follows:

Mild	Discomfort noticed, but no disruption of normal daily activity
Moderate	Discomfort sufficient to reduce or affect normal daily activity
Severe	Incapacitating, with inability to work or to perform normal daily activity

The criteria for assessing severity are different than those used for seriousness (see [Section 9.5.1.6.2](#) for the definition of an SAE).

### **Assessing Relationship to Study Treatment**

Items to be considered when assessing the relationship of an AE to the study treatment are:

- Temporal relationship of the onset of the event to the initiation of the study treatment

- The course of the event, especially the effect of discontinuation of study treatment or reintroduction of study treatment, as applicable
- Whether the event is known to be associated with the study treatment or with other similar treatments
- The presence of risk factors in the study subject known to increase the occurrence of the event
- The presence of nonstudy, treatment-related factors that are known to be associated with the occurrence of the event

#### *Classification of Causality*

The relationship of each AE to the study drug will be recorded on the eCRF in response to the following question:

Is there a reasonable possibility that the study drug caused the AE?

Yes (related) A causal relationship between the study drug and the AE is a reasonable possibility.

No (not related) A causal relationship between the study drug and the AE is not a reasonable possibility.

#### **9.5.1.6.2 SERIOUS ADVERSE EVENTS AND EVENTS ASSOCIATED WITH SPECIAL SITUATIONS**

A SAE is any untoward medical occurrence that at any dose:

- Results in death
- Is life-threatening (ie, the subject was at immediate risk of death from the AE as it occurred; this does not include an event that, had it occurred in a more severe form or was allowed to continue, might have caused death)
- Requires inpatient hospitalization or prolongation of existing hospitalization
- Results in persistent or significant disability/incapacity
- Is a congenital anomaly/birth defect (in the child of a subject who was exposed to the study drug)

Other important medical events that may not be immediately life-threatening or result in death or hospitalization but, when based on appropriate medical judgment, may jeopardize the subject or may require intervention to prevent one of the outcomes in the definition of SAE listed above should also be considered SAEs. Medical and scientific judgment should be exercised in deciding whether expedited reporting is appropriate in such situations.

In addition to the above, events associated with special situations include pregnancy or exposure to study drug through breastfeeding; AEs associated with study drug overdose, misuse, abuse, or medication error. These events associated with special situations are to be captured using the SAE procedures but are to be considered as SAEs only if they meet 1 of the above criteria. All AEs associated with special situations are to be reported on the eCRF whether or not they meet the criteria for SAEs.

All SAEs must be followed to resolution or, if resolution is unlikely, to stabilization.

The following hospitalizations are not considered to be SAEs because there is no “adverse event” (ie, there is no untoward medical occurrence) associated with the hospitalization:

- Hospitalizations for respite care
- Planned hospitalizations required by the protocol
- Hospitalization planned before informed consent (where the condition requiring the hospitalization has not changed after study drug administration)
- Hospitalization for administration of study drug or insertion of access for administration of study drug
- Hospitalization for routine maintenance of a device (eg, battery replacement) that was in place before study entry

#### 9.5.1.6.3 LABORATORY MEASUREMENTS

Clinical laboratory tests to be performed, including hematology, chemistry, and urinalysis, are summarized in [Table 3](#). Subjects should be in a seated or supine position during blood collection. As depicted in the Schedule of Procedures/Assessments ([Table 4](#)), blood for clinical laboratory tests and urine for urinalysis will be collected at Screening. Clinical laboratory evaluations may be performed at other visits, per the investigator’s discretion, if required for assessment of an AE.

**Table 3 Clinical Laboratory Tests**

Category	Parameters
Hematology	Hematocrit, hemoglobin, platelets, RBC count, and WBC count with differential
Chemistry	
Electrolytes	Chloride, potassium, sodium
Liver function tests	Alanine aminotransferase, alkaline phosphatase, aspartate aminotransferase, total bilirubin
Renal function tests	Blood urea/blood urea nitrogen, creatinine
Other	Albumin, calcium, total cholesterol, glucose (fasting), lactate dehydrogenase, phosphorus, total protein, triglycerides, uric acid, lipid profile (fasting).
Urinalysis	glucose, ketones, occult blood, pH, protein, specific gravity, WBCs

RBC = red blood cell, WBC = white blood cell.

A laboratory value that is considered abnormal and clinically significant may meet the criteria to qualify as an AE as described in this protocol (see [Section 9.5.1.6.1](#)) and the eCRF Completion Guidelines. In these instances, the AE corresponding to the laboratory abnormality will be recorded on the Adverse Event eCRF.

#### **9.5.1.6.4 VITAL SIGNS AND WEIGHT MEASUREMENTS**

Vital sign measurements (eg, systolic and diastolic blood pressure [mmHg], pulse [beats per minute], respiratory rate [per minute], body temperature [in centigrade]), weight (kg) and height (cm) will be obtained at the visits designated in the Schedule of Procedures/Assessments ([Table 4](#)) by a validated method. Blood pressure and pulse will be measured after the subject has been sitting for at least 5 minutes. All blood pressure measurements should be performed on the same arm, preferably by the same person.

#### **9.5.1.6.5 EPITRACK**

Cognition will be assessed in subjects 6 years of age and older at Visit 2 (Week 0) and at 3 and 12 month visits (Visits 4 and 7, respectively) using the EpiTrack® assessment tool.

The EpiTrack (second edition with recently extended and revised norms) is a screening tool dedicated to the tracking of adverse cognitive effects of antiepileptic medication ([Lutz and Helmstaedter, 2005](#)). Studies have demonstrated the usefulness of the EpiTrack with regard to cognitive monitoring of the impact of pharmacological treatments ([Lutz and Helmstaedter, 2005](#); [Helmstaedter and Witt, 2008](#); [Helmstaedter and Witt, 2010](#); [Helmstaedter and Witt, 2013](#); [Witt, et al., 2014](#)). The test includes 6 subtests: response inhibition, visuo-motor speed, mental flexibility, visual motor planning, verbal fluency, and working memory. Based on the subtest results, an age-corrected total score is calculated. Higher scores reflect better performance with a maximum score of 49 points. The interval for mild impairment is 29 to 31 points, and the cutoff for significant impairment is 28 points or less. Practice corrected reliable change indices indicate a significant change with a gain of more than 3 points and a loss of more than 2 points.

The EpiTrack Junior will be administered for subjects ages  $\geq 6$  to 16 years old. (revised per Amendment 01)

At the investigator's discretion, a subject may be excluded from the cognition assessments based on their assessment of the subject and the subject's capability to complete the assessment at baseline. If the cognition assessments are not done for a subject, the justification should be recorded in the eCRF.

#### **9.5.1.6.6 BECK DEPRESSION INVENTORY-II**

The Beck Depression Inventory-II (BDI-II) is a 21-question multiple-choice self-report inventory and is widely used for measuring the severity of depression. The depression score will be used to aid in interpretation of the cognition score. The BDI-II will be administered in patients 16 years of age and older who are administered the EpiTrack.

At the investigator's discretion, a subject may be excluded from the cognition assessments based on their assessment of the subject and the subject's capability to complete the assessment at baseline. If the cognition assessments are not done for a subject, the justification should be recorded in the eCRF.

**9.5.1.6.7 PITTSBURGH SLEEP QUALITY INDEX**

The Pittsburgh Sleep Quality Index (PSQI) is a retrospective sleep quality instrument with 19 items (Buysse et al., 1989). It measures subjects' perspectives on sleep parameters (length of sleep, sleep disturbances), sleep quality, and impact on daily functioning. The PSQI will be administered to patients 12 years of age and older.

**9.5.1.6.8 QUALITY OF LIFE IN EPILEPSY INVENTORY-31**

The Quality of Life in Epilepsy Inventory-31 is a survey of health-related quality of life for adults (18 years or older) with epilepsy.

**9.5.1.6.9 COLUMBIA-SUICIDE SEVERITY RATING SCALE**

An assessment of suicidality will be performed using the C-SSRS at the visits designated in the Schedule of Procedures/Assessments (Table 4). The C-SSRS will be administered to patients 6 years of age and older. Subjects under 6 years of age will be clinically monitored for suicidality. (revised per Amendment 01)

**9.5.1.6.10 PREGNANCY TEST**

A urine or serum-hCG pregnancy test will be performed during the Screening Period (Visit 1) and/or at Visit 2 (Week 0), Visit 6 (Week 39) and Follow-Up Visit for premenopausal women and postmenopausal women who have been amenorrheic for less than 12 months.

9.5.1.7 Description of Procedures/Assessments Schedule

The study procedures and assessments are shown in Table 4.

9.5.2 Schedule of Procedures/Assessments

**Table 4 Schedule of Procedures/Assessments in Study E2007-G000-410 (revised per Amendment 01)**

Period	Screening a	Titration b (Wk 0 to Wk 12)				Maintenance b				Early Discontinuation	Follow- Up b,c	Unscheduled d
Study Week(s)	Wk -6 to Wk 0	Wk 0	Wk 2 c	Wk 4	Biweekly f,g	Wk 13	Wk 26	Wk 39	Wk 52		Wk 56	
Study Day		1	15	29		92	183	274	365			
Visit Number	1	2		3		4	5	6	7		8	
Procedure/ Assessment												
Informed consent/assent h	X											
Inclusion/ exclusion criteria	X	X										
Demographic data	X											
Seizure type and frequency	X	X										
Medical history i	X											
Documentation of perampanel dose		X		X	X	X	X	X	X	X		
Concomitant medications	X j	X				X	X	X	X	X	X	X d
Concomitant AED	X j	X				X	X	X	X	X	X	X d
Vital signs	X	X				X	X	X	X	X	X	X d
Cognition assessment (EpiTrack) k		X				X			X	X		

**Table 4 Schedule of Procedures/Assessments in Study E2007-G000-410 (revised per Amendment 01)**

Period	Screening a	Titration b (Wk 0 to Wk 12)				Maintenance b				Early Discontinuation	Follow- Up b,c	Unscheduled d
		Wk -6 to Wk 0	Wk 0	Wk 2 e	Wk 4	Biweekly f,g	Wk 13	Wk 26	Wk 39			
Study Week(s)												
Study Day		1	15	29		92	183	274	365			
Visit Number	1	2		3		4	5	6	7		8	
Procedure/ Assessment												
Depression assessment (BDI-II)		X				X			X	X		
QOLIE-31		X							X	X		
PSQI		X							X	X		
C-SSRS l	X	X				X	X	X	X	X		
Clinical laboratory evaluations m	X								X			
Blood sample for pharmacogenomics		X										
Pregnancy test	X	X n						X		X	X	
Adverse events	X	X		X	X	X	X	X	X	X	X	X
Dispense study drug		X				X	X	X				
Return study drug						X	X	X	X	X		
Study drug compliance						X	X	X	X	X		
Dispense subject diary	X o	X				X	X	X				

**Table 4 Schedule of Procedures/Assessments in Study E2007-G000-410 (revised per Amendment 01)**

Period	Screening a	Titration b (Wk 0 to Wk 12)				Maintenance b				Early Discontinuation	Follow- Up b,c	Unscheduled d
		Wk -6 to Wk 0	Wk 0	Wk 2 e	Wk 4	Biweekly f,g	Wk 13	Wk 26	Wk 39			
Study Week(s)												
Study Day		1	15	29		92	183	274	365			
Visit Number	1	2		3		4	5	6	7		8	
Procedure/ Assessment												
Return and review subject diary		X				X	X	X	X	X		

AED = antiepileptic drug, BDI-II = Beck Depression Inventory II, eCRF = electronic Case Report Form, C-SSRS = Columbia-Suicide Severity Rating Scale, PSQI = Pittsburgh Sleep Quality Index, QOLIE-31 = Quality of Life in Epilepsy Inventory-31, Wk = week.

a: Up to 12 weeks of baseline seizure frequency to be determined at screening; any screening assessments may be repeated during the Screening Period, at the discretion of the investigator.

b: Visit to be done within ±7 days of the schedule. Subjects may continue to receive commercial perampanel during the Follow-Up Period. (revised per Amendment 01)

c: To be completed by subjects who are withdrawn from the study for any reason after Visit 2 (Week 0) and before Visit 6 (Week 39). (revised per Amendment 01)

d: At the unscheduled visit, only the assessments that the investigator(s) judged necessary based on the subject's condition will be performed

e: At the end of Week 2, the perampanel dose increases from 2 to 4 mg; this is not a visit.

f: Telephone Visit; all dose adjustments and rationale for the adjustments, as well as adverse events will be recorded on the eCRF.

g: Follow-up telephone calls to Visit 3 may occur biweekly, or at a frequency of the investigator's discretion. All dose adjustments and rationale for adjustments, as well as adverse events will be recorded in the eCRF.

h: Informed consent/assent may be obtained prior to study start; it must be obtained prior to any study related procedures.

i: All pertinent medical and surgical history within 5 years before Visit 1 (Week 0).

j: Prior and concomitant medication(s) within 24 weeks (and as long as available for AED[s]) before Visit 2 (Week 0).

k: Subjects 6 years and older. EpiTrack Junior will be administered for subjects aged ≥6 to 16 years old. (revised per Amendment 01)

l: The C-SSRS will be administered to patients 6 years of age and older. Subjects under 6 years of age will be clinically monitored for suicidality. (revised per Amendment 01)

m: Any laboratory value that is considered abnormal and clinically significant will be reported as an adverse event. Clinical laboratory evaluations may be performed at other visits if required for assessment of an adverse event. Blood for laboratory evaluations must be collected in fasting state. (revised per Amendment 01)

n: Required only if a negative screening pregnancy test was obtained more than 72 hours before the 1st dose of study drug.

o: Subjects may also provide retrospective seizure frequency history if available.

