#### Maintenance Period

Subjects will continue to receive the perampanel dose level that was administered at the end of the Titration Period, when they enter the 39-week Maintenance Period. Subjects will come to the study site for Visit 4 (Week 13), Visit 5 (Week 26), Visit 6 (Week 39), Visit 7 (Week 52), and at the Follow-Up Visit (Visit 8). All subjects who discontinue the study are to complete the study's early discontinuation procedures indicated in the Schedule of Procedures/Assessments. (revised per Amendment 01)

According to the investigator's clinical judgment, subjects who experience AEs may have their perampanel dose reduced. Conversely, if seizures are not adequately controlled, subjects may have their dose increased up to a maximum of perampanel 12 mg. During the Maintenance Period, subjects whose perampanel dose has been reduced may have the dose increased again, at the discretion of the investigator, as soon as tolerability improves. Subjects who cannot tolerate a dose of 4 mg will discontinue perampanel treatment and be withdrawn from the study. Adjustment of the concomitant AED dose level during the Maintenance Period is permitted. Subjects who receive perampanel as a 1st adjunctive therapy may also be converted to perampanel monotherapy at the discretion of the investigator. All adjustments to concomitant AED dose levels must be reported in the eCRF.

The overall study design is depicted in [Figure 1](#).

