**9.1.4 Follow-Up Period (4 weeks)**

The Follow-Up Period will begin at the end of the Maintenance Period. Subjects may continue to receive commercial perampanel during the Follow-Up Period. (revised per Amendment 01) At the end of the Follow-Up Period, a Follow-Up Visit will take place. Subjects who are withdrawn from the study for any reason will also undergo a Follow-Up Visit.

The end of the study will be the date of the last study visit for the last subject. However, if there are AEs that are present and not resolved at the last scheduled visit, these AEs should be followed to stabilization or resolution.

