### 9.3.3 Removal of Subjects from Therapy or Assessment

#### 9.3.3.1 Scheduled Termination

Subjects will be considered to have completed the Titration Period after up to 13 weeks of titration treatment and completion of the Visit 4 (Week 13) visit procedures. (revised per Amendment 01) Subjects who have completed the Titration Period will enter the Maintenance Period. Subjects will be considered to have completed the Maintenance Period after 39 weeks of maintenance treatment and completion of the Visit 7 (Week 52) visit procedures. Upon completion of the Titration Period, the Maintenance Period, and the Follow-Up Period, and after resolution of any AEs that may be present on the last visit, the subject will be considered to have completed the study.

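### Table 4 footnote c stops at Week 39, but the protocol text requires the same visits of everyone who withdraws up to Week 52

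*Protocol*

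**What the plan says.** Table 4 of the protocol is the schedule that sites work from. Its footnote c, marked as revised under Amendment 01, gives a visit to subjects "withdrawn from the study for any reason after Visit 2 (Week 0) and before Visit 6 (Week 39"). All three pages of the table print the letter c on the Follow-Up column (Week 56, Visit 8). The Early Discontinuation column carries no footnote.

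The body of the protocol sets no week limit on either visit:

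- Section 9.1.4, on the Follow-Up Visit: "Subjects who are withdrawn from the study for any reason will also undergo a Follow-Up Visit".
- Section 9.1.3, on early discontinuation: "All subjects who discontinue the study are to complete the study's early discontinuation procedures". Section 9.5.5 repeats this.
- Section 9.1.3 also sends completers to Visit 8, listing "Visit 7 (Week 52), and at the Follow-Up Visit (Visit 8") among the site visits. Section 9.3.3.1 counts a subject as having completed the study "Upon completion of the Titration Period, the Maintenance Period, and the Follow-Up Period" and after resolution of any remaining adverse events.

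On adverse events (AEs), Section 9.5.1.6.1 says they "should be recorded beginning from the time the subject signs the study ICF through the last visit", and that "SAEs will be collected for 28 days after the last dose". SAP Section 8.2.2 counts AEs as on treatment until 28 days after the last dose.

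**The concern.** The Maintenance Period runs to Visit 7 (Week 52), so a cut-off at Visit 6 (Week 39) leaves out its last 13 weeks. A coordinator who reads the table and not Section 9.1.4 could conclude that a subject withdrawing in Week 45 needs no further visit of the kind the footnote governs.

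What could be lost depends on the column:

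- **Follow-Up column.** Visit 8 could be missed. New non-serious AEs starting after the Early Discontinuation visit could then go unrecorded, although the SAP's counting window is still open. The Visit 8 pregnancy test would also be missed.
- **Early Discontinuation column.** Section 9.1.4 still provides the Follow-Up Visit, so the AE loss does not follow. The end-of-treatment assessments could be lost instead. After baseline, Table 4 schedules QOLIE-31 and PSQI only at Week 52 and at Early Discontinuation, so a late withdrawal who skipped that visit would have no post-baseline value for either. The last EpiTrack, BDI-II and diary return would go too.

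**Working it through.** The plan gives no figure to reproduce. The check compares the texts, and one interval comes from Table 4.

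**Who is covered**

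| Subject | Footnote c | Section 9.1.4 (Follow-Up Visit) | Sections 9.1.3 and 9.5.5 (early discontinuation procedures) |
|---|---|---|---|
| Withdraws after Week 0, before Week 39 | named | yes | yes |
| Withdraws between Week 39 and Week 52 | not named | yes | yes |
| Completes Week 52 | not named | yes, at the end of the Follow-Up Period | not applicable |

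The second row disagrees with the text under either placement, so the result does not depend on where the letter c was meant to sit.

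The third row shows that the footnote cannot be an exclusive rule for the Follow-Up column. That reading would drop completers, whom Section 9.1.3 sends to Visit 8. Footnote b on the same column also says "Subjects may continue to receive commercial perampanel during the Follow-Up Period", which presupposes that subjects reach that period after Maintenance.

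**Length of the uncovered window.** Table 4 puts Week 39 at Day 274 and Week 52 at Day 365.

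- 365 − 274 = 91 days = 13 weeks
- Share of calendar treatment time: 91/364 = 25%
- Share of the Maintenance Period: 13/39 = 33%

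These are shares of time, not of subjects or AEs.

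**Illustrative head count (assumptions, not document figures).** Let d be the proportion withdrawing over 52 weeks and S(t) = (1 − d)^((t/52)^k). The share withdrawing in Weeks 39–52 is S(39) − S(52). I take d from 20% to 40%. I use k = 1 for a constant hazard and k = 0.5 for early-weighted withdrawal, which is plausible because Section 9.1.2 discontinues subjects who cannot tolerate 4 mg by the end of titration.

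| d | k | S(39) − S(52) | × 125 planned | × 50 assumed |
|---|---|---|---|---|
| 0.20 | 1 | 0.0459 | 5.7 | 2.3 |
| 0.40 | 1 | 0.0817 | 10.2 | 4.1 |
| 0.20 | 0.5 | 0.0243 | 3.0 | 1.2 |
| 0.40 | 0.5 | 0.0425 | 5.3 | 2.1 |

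This gives 2.4% to 8.2% of subjects, or about 3 to 10 at 125. SAP Section 7 says enrollment stopped short of the plan, so 125 is an upper bound. Actual enrollment is not stated; at an assumed 50 the range is about 1 to 4. These counts are of late withdrawals, not of missed visits.

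**Longest unrecorded AE period per affected subject.** 28 days, reached only if the Early Discontinuation visit falls on the day of the last dose.

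**The case against.** The footnote says who has the visit; it does not say that nobody else does. Read that way it is incomplete rather than contradictory, and a site can satisfy it and the body text together by doing both visits. The body text is clear in three sections. The column marker is also open to doubt: the first page of Table 4 prints c on Week 2 where the later pages print e, and wording about withdrawn subjects would suit the unmarked Early Discontinuation column better.

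The likely harm is small. The Early Discontinuation visit records AEs, vital signs, C-SSRS and a pregnancy test. Known AEs are followed for 28 days after the last dose or until resolution. Section 9.3.3.2 obliges the investigator to try to follow subjects up for AEs, and Section 9.5.5 requires contact with those who stop attending. The head counts rest wholly on assumptions, and the number of visits actually missed could be zero.

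Most of this stands and limits the size of the point. It does not remove the error. The lenient reading leaves the footnote with no purpose and does not explain why it stops at Week 39. Doubt about the column does not help either, since the mismatch exists under both. One safeguard is also weaker than it looks: Section 9.5.1.6.1 collects serious AEs for 28 days after the last dose, but Section 9.5.4.1 says they must be collected through the last visit.

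**Conclusion.** The concern holds: the footnote is wrong as written, and the error is minor. The Week 39 cut-off disagrees with the protocol text whichever column it governs, and no other part of the documents supports it. It appears to be a wrong cut-off rather than a chosen design, although the documents do not state the intent.

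The only size that comes from the documents is the 91-day window. A lost visit requires a site to read the footnote as exclusive and to prefer it to the body text; the AE loss also requires that it govern the Follow-Up column. The primary endpoint is not affected, because Section 9.5.1.2 takes retention from exposure data. What is exposed is late AE ascertainment or end-of-treatment questionnaire data in a small subset of subjects.

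**What to change.** Reword footnote c so that the Follow-Up Visit applies to all Week 52 completers and to every subject withdrawn at any time after Visit 2 (Week 0). For withdrawals, place it about 4 weeks after the last dose. Section 9.1.4 does not state that timing for them; it is taken from the 4-week Follow-Up Period and the SAP's 28-day AE window. Add a footnote to the Early Discontinuation column saying that its procedures apply to everyone who discontinues before Visit 7 (Week 52).

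Both visits are already in the schedule, so nothing is added for subjects. The cost is one footnote correction and one added note, issued as a sponsor-approved amendment or administrative change under Section 11.1.

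Enrollment has already closed, so the correction helps only subjects still on treatment, if any. If the study is past that point, give one count in the study report: the number of Week 39–52 withdrawals without AE ascertainment to 28 days after the last dose.
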